Statistical analysis plan and sample size calculation

Official Title:

The Effect of Chronic Nitrate Supplementation on Acute Mountain Sickness and Exercise Performance in Hypoxia

NCT number

NCT03101904

Document Date

15/10/2015

High-altitude headache

RM ANOVA

2x4 RM ANOVA = Total of 8 repeated measures

	Av correlation		Meaningful difference	Effect size		Sample size
	Calculated	Table		Calculated	Table	
Hypoxia	0.6	Strong = 0.5	14	0.7	Large = 0.57	14
			10	0.5	Medium = 0.35	23
All data	0.2	Weak = 0.3	14	0.7	Large = 0.49	16
			10	0.5	Large = 0.49	16
4 measures	0.4	Weak = 0.3	10	0.7	Large = 0.49	16

Calculations (4 measures)

Average correlation

		Hypoxic			Normoxic
		4 h	6 h	8 h	8 h
Hypoxic	4 h	1	0.4	0.4	
	6 h		1	0.9	
	8 h			1	-0.3
Normoxic	8 h				1

Average correlation = 0.4

Effect size

Meaningful difference = 10

SD of difference (4-6 h in hypoxia) = 18

Cohen's D = 0.55

Conversion to RM ANOVA effect size = $0.55 / (\text{SQRT}(1-0.4)) = 0.7$

(Stevens, 2002)

A sample size estimation for this analysis indicated that 16 participants were needed to produce an 80% chance of obtaining statistical significance at the 0.05 level (5), based on a minimum important difference of 10 mm (2), a standard deviation of the difference of 18 mm, and an estimated average correlation of 0.4 (data from (3)).

Time to exhaustion

t tests – Means: Difference between two dependent means (matched pairs)

Analysis: A priori: Compute required sample size

Input:	Tail(s)	=	Two
	Effect size dz	=	0.9090909
	α err prob	=	0.05
	Power (1- β err prob)	=	0.8
Output:	Noncentrality parameter δ	=	3.1491833
	Critical t	=	2.2009852
	Df	=	11
	Total sample size	=	12
	Actual power	=	0.8174086

The effect of nitrate supplementation on maximal exercise performance (TTE) was determined by paired samples t-test. A sample size estimation for this analysis indicated that 12 participants were needed to produce an 80% chance of obtaining statistical significance at the 0.05 level for a two-tailed design (1), based on a minimum important difference of 30 seconds and a standard deviation of the difference of 33 seconds (data from (4)). Given the smaller required sample size for this analysis, only 15 participants completed the TTE component of the study.

References

1. **Bland M.** *Determination of sample size*. 4th ed. Oxford: Oxford University Press, 2015.

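### Optional and cheap: report a visit-adjusted estimate beside the plain paired t-test for time to exhaustion, with the number in each order

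*SAP*

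**What the plan says.** The section on time to exhaustion states that "The effect of nitrate supplementation on maximal exercise performance (TTE) was determined by paired samples t-test". The sample size is run for the same paired test, "based on a minimum important difference of 30 seconds and a standard deviation of the difference of 33 seconds". It concludes that "12 participants were needed to produce an 80% chance of obtaining statistical significance", two-sided at 0.05. The section adds that "only 15 participants completed the TTE component of the study". No visit, period or order term is named. The SAP does not give the order of conditions, the number of completers in each order, or any figure for a change between visits.

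**The concern.** TTE is a maximal-effort test done under two conditions, so a change from one visit to the next (practice, for example) is plausible whatever the supplement. If some participants had nitrate first and others second, such a change adds to the nitrate-minus-comparator difference in one group and subtracts from it in the other. A plain paired t-test treats that spread as random error. It also leaves a residual shift whenever the two groups differ in size, and 15 completers cannot split evenly. At stake are the width of the interval and, to a smaller extent, the location of the estimate. A model with a visit term removes both effects of a constant change, and the choice of model belongs to the SAP.

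**Working it through.** **Inputs.** From the SAP: target difference 30 s, SD of the difference 33 s, two-sided 0.05, 15 completers. Assumed, because the SAP does not give them: two orders, the split n1/n2, and P = 10, 20 or 30 s.

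**1. The SAP's own figure.** dz = 30/33 = 0.909. Noncentrality = 0.909 × √12 = 3.149 on 11 df, which gives power 0.8174, as stated. The same test with n = 15 has power 0.905.

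**2. Effect of a visit change on the paired test.** Let n1 participants take nitrate second (difference τ + P + error) and n2 take it first (τ − P + error), with within-order SD σ. Then:

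- expected mean difference = τ + P(n1 − n2)/n
- expected s² = σ² + 4·n1·n2·P²/[n(n − 1)]

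At 8/7 with σ = 33 s and P = 20 s, the shift is 20 × 1/15 = 1.3 s. The expected s² is 1089 + 4 × 56 × 400/210 = 1515.7, so the SD used is about 38.9 s. At P = 10 s, s² is 1089 + 106.7 = 1195.7, an SD of about 34.6 s.

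**3. With a visit term.** The estimate is the mean of the two order-specific mean differences. Its SE is (σ/2)√(1/n1 + 1/n2), which at 8/7 is 16.5 × √(1/8 + 1/7) = 8.54 s on 13 df. The mean of s/σ on 13 df is √(2/13)·Γ(7)/Γ(6.5) = 0.981, so the mean 95% half-width is 2.160 × 8.54 × 0.981 = 18.1 s, whatever the value of P.

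**4. Results at 8/7, σ = 33 s, effect 30 s** (exact: normal mean, noncentral chi-square sum of squares). The power range runs from a shift against nitrate to a shift towards it.

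| P (s) | Shift (s) | Half-width, paired (s) | Half-width, visit term (s) | Power, paired | Power, visit term | Type I error, paired |
|---|---|---|---|---|---|---|
| 0 | 0 | 17.95 | 18.1 | 0.905 | 0.900 | 0.050 |
| 10 | 0.7 | 18.8 | 18.1 | 0.87–0.90 | 0.900 | 0.042 |
| 20 | 1.3 | 21.2 | 18.1 | 0.79–0.86 | 0.900 | 0.024 |
| 30 | 2.0 | 24.7 | 18.1 | 0.64–0.78 | 0.900 | 0.010 |

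**5. Less even splits (P = 10/20/30 s).**

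- 9/6: shift 2/4/6 s; paired half-width 18.8/21.1/24.5 s against 18.4 s; type I error 0.046/0.037/0.026, still conservative.
- 10/5: shift 3.3/6.7/10 s; type I error 0.056/0.066/0.069. Under simple random order, a split of 10/5 or less even has probability 0.30.

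**6. Averaged over simple random order.** The shift averages to zero. Paired type I error is 0.050/0.050/0.051. Paired half-width is 18.8/21.0/24.3 s against 18.8 s with the visit term, so nothing is gained on average at P = 10 s.

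**7. If 33 s already contains P (8/7).** The within-order SD is √(1089 − 106.7) = 31.3 s at P = 10 s and √(1089 − 426.7) = 25.7 s at P = 20 s. Paired power is then 0.90–0.93 and 0.93–0.96, not below plan. The visit term narrows the half-width from 18.0 to 17.2 s at P = 10 s and to 14.1 s at P = 20 s.

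**8. When the term pays.** With σ = 33 s, the mean interval is narrower only if |P| exceeds about 4 s (8/7), 8 s (9/6) or 13 s (10/5).

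**The case against.** The case against is substantial. A paired t-test on two conditions is standard and valid, and it matches the sample-size run exactly. Order, allocation and any familiarisation visit are matters for the protocol, which is not at hand, and the values of P have no source in the SAP. As the SAP uses it, the 33 s is divided into 30 s to give the paired effect size, so it reads most naturally as the total SD of the differences, with any visit change inside it. The visit term can also lose precision: at 10/5 with P = 10 s the half-width is 19.2 s with the term and 18.7 s without it.

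All of this stands, and it rules out two stronger inferences. A reader might infer that the stated test is biased or gives too many false positives. The document does not support that: over random order the test is unbiased at about 5%, and at 8/7 and 9/6 it is conservative. Excess error needs 10/5 or worse together with a real visit change, and the SAP shows neither. A reader might also infer that TTE is underpowered. That needs 33 s to exclude P, which the SAP does not say, and the stated n = 12 is correct on its own inputs.

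What the objection does not remove is that the SAP fixes the analysis model, and that an adjusted estimate beside it costs little.

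**Conclusion.** An optional improvement, not an error in the plan. It is conditional on two orders of conditions. The size then depends on P and on the split, neither of which the SAP gives. For a near-even split the shift is small, at most 2 s for P up to 30 s against a 30 s target, and the main loss is width: at 8/7 about 4% at P = 10 s (18.8/18.1) and 17% at P = 20 s (21.2/18.1), if 33 s is the within-order SD. If 33 s includes P, planned power stands and only a narrower interval is to be gained. The algebra is certain; how much it matters in this trial cannot be judged from the SAP. A visit term deals only with a constant change. It does not remove carryover or learning that differs between people.

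**What to change.** - **If the TTE data have been seen**, as the past tense suggests: keep the stated paired t-test as the main result. Beside it, report the supplement effect and 95% CI from a linear model with participant, supplement and visit (n − 2 df), and the number of completers in each order.
- **If the data are unseen**: make that model the main TTE analysis, with the paired t-test as a sensitivity analysis.
- **If all participants had the same order**: say so, and state that supplement and visit cannot be separated.

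The cost is a few lines of SAP text, each participant's order of conditions, and one degree of freedom. If there is no visit change, power with the term goes from 0.905 to 0.900 at 8/7, 0.890 at 9/6 or 0.866 at 10/5.
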